### **Liver Substudy Outcome Measures**

The primary endpoint is a decrease in ALT 12 months after completion of phlebotomy. For this endpoint, we will include as a separate analysis individuals in Aim 1 with elevated ALT attributed to NASH (by exclusion of viral hepatitis, etc.) but who elected not to participate in Aim 2.

Secondary endpoints will include improvements (or decreased deterioration) compared to controls in: (1) Model of End-stage Liver Disease (MELD) scores (64) as determined from the history and serum testing; (2) Fibroscan and MRI indices of hepatic fibrosis; (3) ALT and imaging indices will analyzed as a function of hepatic iron, change in hepatic iron, hepatic stiffness, and hepatic fibrosis, and using initial, final, and change in ferritin as a continuous variables, to interrogate possible optimal thresholds and targets for therapy.

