### **Subjects selection criteria**

Subjects will have type 2 diabetes mellitus, or prediabetes, defined by HgbA1C criteria.

- **Inclusion Criteria.** Ages 40-75; At least 3 months since diagnosis of prediabetes or diabetes; HgbA1C value within three months or at screening of 5.7-6.4% for those with prediabetes, undiagnosed on no medication HgbA1C 6.5-6.9 and 7-8.5% for those with diabetes (the upper limit of the latter to reduce the likelihood of major changes in glycemic intervention during the trial period, and the lower limit to allow some room for improvement); Serum ferritin levels within 1 year or at the time of screening in the upper half of the normal range (>50 ng/mL for women and >100 ng/mL for men). C-reactive protein levels up to 11.0. Subjects will be on stable lifestyle therapy and 0-2 antihyperglycemic agents that are non-hypoglycemic (i.e. no sulfonylureas, glinides or insulin) to limit the chances of hypoglycemia if, as hypothesized, participants become more insulin sensitive with iron reduction. Aim 2 – serum ALT> 1.5 times the upper limit of normal, or; liver stiffness of > 12.5 kPa by Fibroscan transient elastography.
- **Exclusion Criteria.** Documented current anemia, hemoglobin levels within 0.5 g/dL of the lower limit of normal (<12.5 g/dL for women and 13.5 g/dL for men), or recent blood loss; bleeding diatheses (coagulation abnormalities or treatment with anticoagulants); serious chronic infections or chronic inflammatory conditions that could elevate ferritin as an "acute phase reactant;" C-reactive protein greater than 10.0, the upper limit of normal, to further validate the lack of significant chronic inflammation; active cancer diagnosis (excluding skin cell cancers other than melanoma); renal insufficiency (eGFR<60 ml/min); history of orthostatic hypotension; heavy alcohol use (NIH criteria, for men greater than 4 drinks on any day or 14/week, for women >3 drinks on any day or > 7/ week); pregnancy or premenopausal women of childbearing age, unless unable to become pregnant because of oral contraceptive use, IUD, birth control implants, surgical loss of ovaries or uterus. Aim 2 – individuals meeting the additional inclusion criteria for aim 2 will be tested for anti-HAV IgM, HBs Ag, anti-HBc. IgM, anti HCV IgM and IgG. Subjects who prove positive for any of these viral serologies, except for HCV IgG will be excluded. The latter will be tested for HCV RNA by PRC, and if negative they will be eligible for enrollment

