- c. Visit 2 (7-14 days) (fasting) (~1 hr):** Report to the Clinical Research Unit (CRU) at University of North Carolina at Chapel Hill (UNC) or Wake Forest (WF) School of Medicine. Review Adverse Events (AE's). Measure outcome variables (weight, blood pressure; blood for, insulin, lipid panel, CMP (14), Ferritin) and the Ultrasound Fibroscan (WFBH site only). Subjects who complete Visit 2 will be compensated \$50 for their time.

*Randomization* (1:1) to control (sham phlebotomy) or phlebotomy groups with final target ferritin levels of 20-40 ng/ml for males and 20-40 for females. Phlebotomy will not be performed if hemoglobin is lower than 12.5 g/dL for women and 13.0 g/dL for men; in that case, subjects will undergo repeat hemoglobin measurement every 2 months. If the hemoglobin value increases above the threshold for phlebotomy at Visits 3 or 4, phlebotomy will be performed; otherwise, participants will have an “end of study” visit 1 at six months. If blood pressure declines by > 20 mm Hg systolic, or pulse increases by > 30 bpm upon standing, phlebotomy will not proceed.

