- **e. Visit 4 (not fasting):** Review AE's. Draw blood for ferritin and perform on site determination of hemoglobin. If hemoglobin is lower than 12.5 g/dL for women and 13.0 g/dL for men, phlebotomy will not be performed and subject will be scheduled 8 weeks out for Visit 5. At this visit, after the sham phlebotomy, all of the Placebo Group will be scheduled to the “end of study” sequence. Three phlebotomies were the average needed for the treatment group in the pilot study to achieve goal ferritin. If serum ferritin results of the treatment group subjects from this visit have reached the target range (20-40 ng/ml), the subject will be moved to the End of Study sequence. If not, the subject will continue to Visit 5. Subjects who complete Visit 4 will be compensated \$50 for their time.
- **f. Visits 5-6, if needed (not fasting):** Hemoglobin and Ferritin will be drawn. If hemoglobin is lower than 12.5 g/dL for women and 13.0 g/dL for men, phlebotomy will not be performed and subject will be scheduled 6 months out to start the End of Study sequence. If the serum ferritin results from Visit 5 have reached the target range (20-40 ng/ml), the subject will be moved to the End of Study sequence. If not, the subject will continue to Visit 6. After Visit 6, all subjects, regardless of serum ferritin results, will move to the End of Study sequence. Subjects who complete these visits will be compensated \$50 for their time per visit.
- **g. End of Study Visit 1 (6 months ± 2 weeks after last phlebotomy visit) (fasting) (~1 hr.):** Patient should come in fasting. Review AE's. Perform outcome measures (blood pressure, weight, CMP (14), CBC platelets no diff., insulin, HgbA1C, CRP, lipid panel, ferritin. Fibroscan (WFBH site only), place CGM, which the subject will mail back in a prepaid mailer. Subjects who complete this visit will be compensated \$100 for their time.

- **h. End of Study Visit 2 (6 months  $\pm$  2 weeks after E.O.S. 2) (fasting) (~1 hr.):** Patient should come in fasting. Review AE's. Perform outcome measures (CGM placement, blood pressure, weight, CMP (14), CBC platelets no diff., insulin, lipid panel, HgbA1C, ferritin, CRP, Fibroscan (WFBH site only)). Place CGM, which the subject will mail back in a prepaid mailer. Subjects who complete this visit will be compensated \$100 for their time.

- Study procedure: Liver Substudy
- The Screening Visit and Visit 1 will be the same as the Basic Study

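### MELD is a liver-substudy secondary endpoint, but no PT/INR is scheduled at any visit, so the score cannot be derived from the planned tests

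*Combined protocol and SAP*

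**What the plan says.** In the combined protocol and SAP, Liver Substudy Outcome Measures introduces the list with "Secondary endpoints will include improvements (or decreased deterioration) compared to controls in". Item (1) is "Model of End-stage Liver Disease (MELD) scores (64) as determined from the history and serum testing". Item (2) is the Fibroscan and MRI indices of fibrosis. No MELD formula, version or laboratory source is given.

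The laboratory work is set out under Interventions and Interactions, in the Basic Study table and the visit descriptions:

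- Visit 2 (baseline): "Measure outcome variables (weight, blood pressure; blood for, insulin, lipid panel, CMP (14), Ferritin) and the Ultrasound Fibroscan (WFBH site only").
- End of Study Visit 1: "Perform outcome measures (blood pressure, weight, CMP (14), CBC platelets no diff., insulin, HgbA1C, CRP, lipid panel, ferritin".
- End of Study Visit 2: "Perform outcome measures (CGM placement, blood pressure, weight, CMP (14), CBC platelets no diff., insulin, lipid panel, HgbA1C, ferritin, CRP".

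The liver substudy text and calendar add only MRI and Fibroscan to these. The Aim 2 eligibility text adds viral serologies.

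Subjects selection criteria excludes "bleeding diatheses (coagulation abnormalities or treatment with anticoagulants") and "renal insufficiency (eGFR<60 ml/min"). Entry to Aim 2 is by ALT above 1.5 times the upper limit of normal or by liver stiffness above 12.5 kPa. No bilirubin limit is stated.

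**The concern.** An endpoint that is to be compared between arms needs all its components at baseline and at follow-up. MELD as commonly understood needs an INR, and the schedule contains none. If the protocol is followed as written, the MELD line of the results has no data behind it. That cannot be put right at the analysis stage, because a coagulation time that was never measured cannot be imputed from a metabolic panel.

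A second, weaker issue is whether the score would be informative if the test were added. The population is selected to have no known coagulation disorder and an eGFR of at least 60, and the score has a hard floor.

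**Working it through.** The plan states no MELD effect size, SD or power, so there is no figure to reproduce. The check has three parts.

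**1. Components against schedule.** Assumptions: MELD is the three-component score, and a 14-test metabolic panel has its usual content (bilirubin, creatinine, AST, ALT).

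| Component | Visit 2 | EOS 1 | EOS 2 |
|---|---|---|---|
| Bilirubin | CMP (14) | CMP (14) | CMP (14) |
| Creatinine | CMP (14) | CMP (14) | CMP (14) |
| INR | none | none | none |

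The screening visit and Visits 3 to 6 contain no coagulation test either. The planned tests therefore give a complete score at 0 of 3 outcome time points for any of the roughly 40 participants. The visit table, the visit text and the liver calendar agree on this, so a lost table row is an unlikely explanation.

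**2. Where the score would start if INR were added.** Assumed formula, with any value below 1 set to 1:

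MELD = 3.78 ln(bilirubin) + 11.2 ln(INR) + 9.57 ln(creatinine) + 6.43

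- Floor (all components at 1): 6.43.
- Creatinine: under CKD-EPI 2021 (assumed), an eGFR of 60 corresponds to about 1.25 mg/dL in a man of 75 and 1.50 in a man of 40, and to 0.98 and 1.18 in women of the same ages. The most that creatinine can add at entry is therefore 2.1 to 3.9 points in men and 0 to 1.6 in women. For example, 9.57 × ln(1.5) = 3.9.
- INR: an assumed entry range of 1.0 to 1.2 adds 0 to 2.0 points (11.2 × ln(1.2) = 2.0).
- Bilirubin: eligibility sets no limit. Values of 1.2, 2 and 3 mg/dL add 0.7, 2.6 and 4.2 points.

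Combined, with INR 1.0 to 1.2 and creatinine 1.0 to 1.5:

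- Bilirubin 1: 6.43 up to 6.43 + 2.04 + 3.88 = 12.35, that is 6.4 to 12.4.
- Bilirubin 3: add 4.15 to both ends, giving 10.6 to 16.5.

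A participant at the floor has no room to improve. One with creatinine or bilirubin above 1 mg/dL, or INR above 1, has some.

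**3. Would a blood-based fibrosis index be a clean replacement?** FIB-4 (formula assumed) is age × AST / (platelets × √ALT). All its laboratory inputs are scheduled, although baseline platelets are drawn at screening while AST and ALT are drawn at Visit 2. Using the pre- and post-phlebotomy means in Table 1 of the background section, and holding age and platelets fixed:

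- ALT 64 to 36 alone: √64 / √36 = 8/6 = 1.33, so FIB-4 rises by about 33%.
- With AST 41 to 28 as well: 1.333 × 28/41 = 0.91, a net fall of about 9%.

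A fall in ALT, which is the substudy's primary endpoint, therefore pushes FIB-4 in the unfavourable direction. FIB-4 is not a straightforward substitute.

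**The case against.** The strongest defence is that the plan does not limit MELD to the visit bloods. It names history as a source, and blood for research storage is collected at screening, Visits 2 to 6 and both End of Study visits. This shows that an INR might exist for some participants, so it would be wrong to say that nobody could ever have a score. It does not close the gap. The plan provides for no extraction of INR from records and specifies no tube type or coagulation assay for the stored blood. Any chart value would be incidental and not timed to the visits.

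It can also be said that the plan never defines MELD. It cites a reference numbered 64, and the list available to me stops at 40. I do not count that against the plan, but the three-component reading remains an assumption on which the whole point rests.

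A reader might go further and infer that MELD could not show improvement or separate the arms, because eligibility removes most of its range. The documents do not support that:

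- The endpoint counts reduced deterioration as well as improvement, and entry criteria do not cap later worsening.
- Bilirubin is unrestricted, and the stiffness route can admit advanced disease.
- Creatinine can exceed 1.0 mg/dL at an eGFR of 60 or more.
- With no coagulation test at screening, the coagulation exclusion can act only on what is already known. It does not establish a normal INR in everyone enrolled.

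Finally, this is one secondary item in an optional, single-site substudy. Its position at the head of the list is not stated to confer priority.

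**Conclusion.** The scheduling gap is real. On the standard definition of MELD, one of the three components has no scheduled source at baseline, EOS 1 or EOS 2, and the endpoint cannot be derived from planned tests in the roughly 40 liver-substudy participants. This rests on the assumed three-component formula and the usual content of the metabolic panel.

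The sensitivity point is secondary and a matter of likelihood. Under the assumed entry values, many participants would probably start near 6.43. With about 40 people in two arms the endpoint would be insensitive, though not incapable of showing a difference. The documents give no distribution of bilirubin, INR or creatinine, so the share of participants at the floor cannot be stated.

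The importance is low. The ALT primary endpoint, the imaging indices and the main trial are unaffected.

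**What to change.** Choose one of the following by amendment:

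1. Keep MELD. Add PT/INR to the blood draws already taken at Visit 2, EOS 1 and EOS 2 for liver-substudy participants, state the MELD version, and report values and changes by arm descriptively. The cost is one extra tube per draw, at most 40 × 3 = 120 samples.
2. Delete MELD and rely on the Fibroscan and MRI indices already listed. The cost is a shorter endpoint list.

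If FIB-4 is reported from the scheduled bloods, label it exploratory, name the screening platelet count as the baseline value, and state that a fall in ALT by itself raises the index.

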### **Glucose Mechanisms Substudy Outcome Measures**

Our primary endpoint will be an improvement in the FSIGTT DI, which is the best predictor of diabetes of the many indices arising from MinMod analysis of FSIGTT data (41). Secondary analyses will be the indices that directly quantify the two hallmarks and principal pathogenic factors in T2DM, namely insulin secretory capacity (AIRg) and insulin sensitivity (Si). As in Aim 2, and as in the pilot study on which this Aim is modeled, we will pool the diabetes and prediabetes groups for the primary analysis. This study is powered for that group analysis based on our preliminary data, although we will subanalyze by subgroups and with ferritin, AIRg, and Si as continuous variables to determine if there is evidence for an optimal ferritin target.

### **Analytical Plan**

#### **Statistical Plan and Data Analysis.**

The primary analysis will be an analysis of covariance to compare the mean change in the primary endpoint for each aim (HgbA1C at 6 months after phlebotomy for Aim 1, serum ALT at 12 months after phlebotomy for Aim 2, and DI at 6 months after phlebotomy for Aim 3) between the iron depletion and control groups in the full cohort of patients after controlling for the baseline levels of those measurements. The baseline HgbA1C is included as a covariate to increase study power by accounting for regression to the mean between the two time points.

*Secondary Analyses.* The effects of iron depletion on secondary continuous outcomes will be evaluated using analysis of covariance with adjustment for the baseline level of the factor being analyzed as well as the baseline HgbA1C level. For example, we will determine the degree of response (e.g. change in average glucose by CGM) as a function of starting ferritin, ending ferritin, and change in ferritin for determination of dose-response relationships. Treatment effects on dichotomous outcomes (e.g., conversion of pre-diabetes to diabetes) will be evaluated by exact logistic regression, controlling again for the baseline level of the analyzed factor. Ordinal logistic regression will be applied to compare categorical variables with more than 2 ordered categories. In expanded models, interaction terms between the treatment assignment and baseline HgbA1C level will be added to evaluate if the treatment effect differs across the HgbA1C range, and, in particular, between the diabetic and pre-diabetic patients in the study.

*Statistical Power.* In our pilot study of the effects of phlebotomy, we did not measure HgbA1C, but did perform glucose tolerance testing where the difference in area under the curve from pre- to post-treatment was  $1130 \pm 1970$  mg-min/dl. Assuming this average change would be maintained through the day, and converting this change to the relative change in HgbA1C, the change would be expected to be a decrease of  $\sim 0.6$ . With the variance observed, this means a sample size of 32 patients in each group will provide 80% power to detect a difference between the beginning and final HgbA1C in either treatment group at  $p < 0.05$  when pre- and post-phlebotomy results are compared within subjects. This agrees with the published results from another group using HgbA1C, wherein they achieved a significant change ( $p < 0.001$ ) with an N of 31, but a shorter observation period and much less reduction in ferritin (28). A larger sample size (60/group, diabetes and prediabetes, control and phlebotomy) will be recruited to facilitate possible subgroup analysis (e.g. stratification by age, treatment, race, sex) and to allow for dropout. (Previous studies requiring FSIGTT at WF, had dropout rates were in the 12-15% range; in our pilot study, there were none.) Thus, we will be theoretically powered to analyze each target ferritin group separately, although the initial analysis will pool the two treatment groups.

The N for the change in transaminase levels by the same criteria (Aim 2) is 13, and in DI (Aim 3) is 16. Because the natural history is for both glycemia and NAFLD/NASH to deteriorate over time, the comparison of the control group with the treated group should be even more robust.

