## METHODS AND MEASURES

**DESIGN:** We propose a randomized, placebo-controlled trial to determine if reducing tissue iron stores by phlebotomy (blood donation) will improve measures of glycemia in Type 2 Diabetes (T2DM) or prediabetes. Adult subjects (N=240 total) aged 40-75, half with prediabetes and half with early T2DM (controlled by diet or up to 2 nonhypoglycemic agents) with ferritin values in the upper half of normal will be randomized to receive real or sham phlebotomy (blood donation), performed in the same manner as at Red Cross donation centers. Glycemia will be assessed by HgbA1C (primary endpoint), fasting glucose, and continuous glucose monitoring (CGM) before and after treatment. Glycemic outcomes will be assessed 6 and 12 months after achieving the target ferritin. The primary endpoint for which this study aim is powered is a change in HgbA1C at 6 months. As secondary outcomes, we will determine if that improvement is stable over a year, and if there are changes associated with iron reduction in serum alanine transaminase (index of NASH), insulin sensitivity by homeostasis model assessment (HOMA-IR), weight, lipids, blood pressure, changes in the number of diabetes medications for participants with diabetes, and changes in glycemic status (normal, prediabetes or diabetes) for participants with prediabetes. We will also correlate the degree of change in glycemia with the starting ferritin levels and the overall change in ferritin to determine targets and thresholds for iron reduction.

There will be two optional sub studies that will be conducted only at Wake Forest Baptist Medical Center. One will look more closely at liver complications of diabetes and the other will explore whether improvements in glucose levels are due to more insulin production or improved insulin action.

Iron may also play a role in the progression of fatty liver to scarring and cirrhosis. Since 75% of people with diabetes have some degree of fatty liver, we would also like to study how your liver reacts to the lowering of iron.

This will require some additional test, namely an MRI and a liver Ultrasound (Fibroscan). There will be approximately 40 people recruited at Wake Forest Baptist Medical Center for the liver sub study.

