*Phlebotomy:* Both groups will have a sleep mask-style blindfold placed or a barrier (e.g. a towel) will be placed between all subjects and the phlebotomy bag in order to prevent the subject from knowing if blood was drawn, and have a phlebotomy needle placed, usually in an antecubital vein. The treatment group will have 1 Unit (~500 mL) of blood removed, while in the placebo group the needle will remain clamped. After the usual 8-10 minutes required for removal of the unit, both groups will have the needle removed, be given a zero-calorie rehydration drink (12 oz) and remain seated for at least 5 min or until comfortable to stand. A snack will be offered. Blood pressure will be monitored after the procedure and if there is hypotension by the above criteria (see *Randomization*), the subject will be asked to remain another 5-10 min and encouraged to finish the drink or have a second. The phlebotomies or sham phlebotomies will be performed by research nurses in the CRU, who have the training and support to respond to a medical emergency. For considerations related to phlebotomy safety and the use of the placebo group, please refer Visit 3. *WFBH participants only:* The discarded phlebotomy blood will be de-identified and will be picked up by a representative from the [name], the sample will be stored in the Olin Physical Lab on the Reynolda campus, room 216. The blood will be used for in vitro experiments aiming to prevent thrombosis in extracorporeal circulation devices. An Institutional Review Board (IRB) must also approve any future research study using your blood sample.

*Review of laboratory findings:* Ferritin results will not be routinely available prior to phlebotomy, but will be reviewed 1-3 days after the visit. Once the serum ferritin results reach the target range (20-40 ng/ml), the subject will be moved to the End of Study sequence.

- **d. Visit 3 (8 weeks after Visit 2) (not fasting) (~1 hr.):** Review AE's. Draw blood for ferritin and perform on site determination of hemoglobin. If hemoglobin is lower than 12.5 g/dL for women and 13.0 g/dL for men, phlebotomy will not be performed and subject will be scheduled 8 weeks out for Visit 4. If the serum ferritin results from this visit have reached the target range (20-40 ng/ml), the subject will be moved to the End of Study sequence. If not, the subject will continue to Visit 4. Subjects who complete Visit 3 will be compensated \$50 for their time.

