### **Outcome Measure(s)**

The primary endpoint will be an improvement in glycemia as assessed by HgbA1C at the first end of study visit, 6 months after phlebotomy. Acutely, HgbA1C will be lowered by blood donation, because that test measures the lifetime exposure of a red blood cell (RBC) to glucose; phlebotomy will result in new RBC synthesis and hence younger RBC, but that effect should disappear soon after the normal RBC lifespan of ~3.5 to 4 months, well before the first post-treatment assessment at 6 months.

A secondary endpoint will be HgbA1C at 12 months to probe longevity of the effect. Based on animal data, we expect that value to be further improved relative to 6 months, but we have no human data on which to support that hypothesis. We do not anticipate that the effect will decline over that time based on reaccumulation of iron. This is a slow process: In individuals with hemochromatosis, for example, iron overload and its adverse effects may not appear until the 5th or 6th decades. In fact, we even anticipate continued improvement as the high levels of tissue iron redistribute and re-equilibrate as processes triggered by decreasing iron proceed, such as autophagy of ferritin complexes, and unloading of macrophages in the face of low hepcidin (Fig. 1).

Fasting glucose will also be assessed at 6 and 12 months after phlebotomy, with secondary endpoints being an improvement at 6 and 12 months. CGM will also be performed using the Abbott Freestyle Libre Pro system for 7-14 days to enhance validation of HgbA1C measures; it allows determination of multiple fasting levels, daily average glucose and various indices of glucose excursions, e.g. postprandial maxima and areas under the curve.

Other secondary endpoints include improvement in insulin sensitivity (decreased HOMA-IR calculated from fasting glucose and insulin), discontinuation of oral antihyperglycemic agents because of improved HgbA1C, change in ALT, changes in weight or blood pressure, and conversion from prediabetes (HgbA1C criteria) to either diabetes or normal glucose tolerance. The secondary endpoints were chosen because they are inexpensive and frequently assessed as part of usual clinical care, and because of the literature suggesting that they are also improved by phlebotomy. Outcomes will also be analyzed using initial, final, and change in ferritin as a continuous variable to interrogate possible optimal thresholds and targets for therapy.

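### Ferritin targets are to be inferred from ending and change in ferritin, which randomisation does not protect, while the treatment-by-baseline-ferritin interaction is not planned

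*Combined protocol and SAP*

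**What the plan says.** The Objectives text lists threshold and target iron levels among the things the trial will provide. Three places say how:

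- Methods and Measures, Design: the investigators will "correlate the degree of change in glycemia with the starting ferritin levels and the overall change in ferritin to determine targets and thresholds".
- Outcome Measure(s): "Outcomes will also be analyzed using initial, final, and change in ferritin as a continuous variable to interrogate possible optimal thresholds and targets for therapy".
- Statistical Plan and Data Analysis, Secondary Analyses: the example given is "change in average glucose by CGM) as a function of starting ferritin, ending ferritin, and change in ferritin for determination of dose-response relationships".

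The Liver Substudy outcomes repeat the approach with initial, final and change in ferritin. The Glucose Mechanisms Substudy outcomes look for evidence of an optimal ferritin target.

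Under Visit 2, Randomization, allocation is 1:1 to sham or to "phlebotomy groups with final target ferritin levels of 20-40 ng/ml for males and 20-40 for females". The stopping rule is "Once the serum ferritin results reach the target range (20-40 ng/ml), the subject will be moved to the End of Study sequence". Treated patients can leave from Visit 3 onward, and Visit 6 is the last procedure whatever the ferritin. Low hemoglobin defers phlebotomy and, at Visits 5-6, ends it. All controls leave after Visit 4. The first end-of-study visit is timed from the last phlebotomy visit.

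The only interaction named is treatment by baseline HgbA1C. The plan does not say which arms enter the ferritin models, whether a treatment term is included, which visit supplies ending ferritin, or that these results are exploratory.

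**The concern.** The three ferritin variables differ in kind. Starting ferritin is measured before treatment. Ending and change in ferritin are consequences of treatment and of how the patient responded to it: starting level, fall per unit, hemoglobin deferrals and the cap on visits. With one target range, nobody is randomised to a different target.

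That leaves two ways to fit the planned models, each with a weakness. If the arms are pooled without a treatment term, treated patients have large falls and controls have little or none, so the slope picks up the arm difference. If only the treated arm is used, the slope compares patients who fell further with patients who fell less, and anything that affects both ferritin response and glycemia confounds it. Two candidates are visible in the documents: sex, because pilot women started lower and fell less in absolute terms, and elapsed time, because patients needing more procedures are assessed later.

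At stake is a stated aim. An arm difference or a confounded association could be reported as a ferritin dose-response. Meanwhile the question that randomisation can answer, whether the treatment effect varies with starting ferritin, is not pre-specified.

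**Working it through.** The plan gives no figure for these analyses. Its 32 per group is for a within-subject comparison and does not bear on this point.

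**1. Does titration fix ending ferritin?** Pilot means (section 1.E) give ending ferritin of 219 - 150 = 69 ng/mL in men and 92 - 56 = 36 in women. If the average 3.4 units applies to each sex (assumption), the fall per unit is 150/3.4 = 44 and 56/3.4 = 16 ng/mL. As a proportion, the fraction kept per unit is (69/219)^(1/3.4) = 0.712 in men and (36/92)^(1/3.4) = 0.759 in women. With at most five procedures (Visits 2-6), the start value above which 40 ng/mL is not reached is:

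- men: 40 + 5 x 44.1 = 261 (linear) or 40/0.712^5 = 219 (proportional);
- women: 40 + 5 x 16.5 = 122 (linear) or 40/0.759^5 = 159 (proportional).

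So the rule drives ending ferritin and leaves real spread.

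**2. How closely does change in ferritin track arm?** Take men only, with mean fall 150 in the treated arm, no change in controls (assumption) and 1:1 allocation. The correlation of change with arm is 75/sqrt(75² + s²/2), where s is the treated-arm SD of change. The pilot gives ± 33 without saying whether that is an SD or a standard error.

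- s = 33: 75/sqrt(5625 + 544.5) = 0.95.
- s = 33 x sqrt(9) = 99 (a standard error with nine men): 75/sqrt(5625 + 4900.5) = 0.73.

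**3. What does a flat effect look like in the pooled slope?** Use 240 less 20% dropout = 192, or 96 per arm, and an SD of HgbA1C change of 0.7 (assumption). The standard error of the arm difference is 0.7 x sqrt(2/96) = 0.101. An effect of 0.3 units gives z = 0.3/0.101 = 2.97. The pooled slope has expected z of roughly correlation x 2.97, that is 2.17 to 2.84, so it would be significant in about 58% to 81% of trials although the effect does not depend on ferritin.

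**4. Simulation of the visit schedule and stopping rule.** There were 500 trials per scenario and 192 analysed, all models adjusted for baseline HgbA1C. Assumptions not in the documents: 60% men, lognormal starting ferritin, about 72.5% of ferritin kept per unit, 12% hemoglobin deferral per visit, SD 0.7, and an optional unmeasured factor acting on both ferritin response and outcome (outcome loading 0.15 or 0.30). Share of trials with p < 0.05:

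| Scenario | Slope | Result |
|---|---|---|
| Flat effect -0.3 / -0.6, no shared factor | pooled, change | 53% / 98% |
| Same | pooled, ending | 41% / 92% |
| No effect, shared factor 0.15 / 0.30 | treated arm, change adjusted for start | 17% / 64% |
| Same | treated arm, ending | 14% / 53% |
| No effect, no shared factor | all four ferritin slopes | 5-6% |
| All scenarios | treatment x starting ferritin | 4-6% |

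The Monte Carlo standard error at 5% is sqrt(0.05 x 0.95/500) = 1 percentage point. The interaction was fitted on untransformed ferritin without sex, and no scenario let the true effect vary with ferritin, so this row shows error control only.

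**5. Timing.** Visits are 8 weeks apart. The first end-of-study visit therefore falls at 8 + 26 = 34 to 32 + 26 = 58 weeks from Visit 2 in treated patients and 16 + 26 = 42 weeks in controls, each ± 2 weeks. Units removed and elapsed time are linked.

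**The case against.** The strongest reply is that these are secondary analyses, that starting ferritin is already among the regressors, and that much of the wording is cautious: Outcome Measure(s) speaks only of possible thresholds, and the Glucose Mechanisms Substudy asks whether evidence exists. That is fair. Only the Design and Secondary Analyses wording claims determination. But naming starting ferritin as a regressor does not make it an interaction with treatment, and a main-effect slope on starting ferritin does not say who benefits.

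A reader might infer more than the documents support, in three ways.

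- *That titration fixes ending ferritin.* It does not. The Visit 6 cap, the hemoglobin rule and a ferritin result that arrives after the unit may already have been drawn all leave spread. Pilot men averaged 69 ng/mL at the end. Table 1, in a different population treated to 50 ng/mL, shows 47 ± 52. In the simulation about 53% of treated patients ended at or below 40.
- *That change and starting ferritin are too collinear to separate.* If ending ferritin is independent of start, with a starting SD of 96 (32 x sqrt(9), reading the pilot ± as a standard error), the correlation is 96/sqrt(96² + s²): 0.95 at an ending SD of 30 and 0.88 at 52. With capped titration the simulation gives about 0.8. The documents give no ending SD for this regimen, so no collinearity figure should be claimed.
- *That the dose-response models cannot be valid.* With no treatment effect and no shared cause, every slope held its nominal error. The inflated treated-arm rates depend on assumed loadings. C-reactive protein screening is meant to limit inflammation, one possible shared cause.

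**Conclusion.** The point stands in this form. Ending and change in ferritin are post-randomisation and response-driven, and no contrast between targets is randomised. A pooled slope without a treatment term mostly restates the arm difference: by the rough calculation for men and by simulation, a flat effect of 0.3 units would appear as a significant slope on change in ferritin in roughly half to four-fifths of trials. A treated-arm slope rests on an assumption that the plan does not state and the data cannot test. The simulated rates show direction and rough size only, since several inputs are assumed.

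It would be wrong to read this as a flaw in the primary analysis. The ANCOVA of HgbA1C at 6 months does not use ferritin as a regressor and is untouched. Nor is the use of starting ferritin at fault; it is the right variable and needs to enter as an interaction with treatment. The change should be made, but the trial's main conclusion does not depend on it.

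**What to change.** In the Secondary Analyses paragraph:

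1. Pre-specify treatment x baseline log-ferritin in the ANCOVA, with sex in the model, and report the treatment effect across baseline ferritin with 95% confidence intervals. Use the Visit 2 value, since the eligibility ferritin may be up to a year old.
2. Do not pool arms for ending or change in ferritin without a treatment term. Keep those models as exploratory, non-randomised, within-arm description, adjusted for baseline ferritin and sex. State which visit defines ending ferritin. Starting, ending and change are linearly dependent, so at most two can enter one model.
3. Remove wording in Design and Secondary Analyses that these models determine a target or a dose-response, and align Outcome Measure(s) and both substudy outcome sections.
4. Sample Size and Statistical Power refer to separate target ferritin groups, while the Randomization text has one range. These passages must be reconciled.

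No new data are needed. The cost is a more modest claim about targets, and the interaction has limited precision. With SD 0.7 and 96 per arm, its standard error per SD of baseline log-ferritin (within sex) is about 0.7 x sqrt(2/96) = 0.101, so 80% power needs about 2.8 x 0.101 = 0.28 HgbA1C units per SD, nearly half of the 0.6 units the plan expects overall. This scales with the assumed SD, and is a reason to report intervals and not only a p-value.
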